#### **10.1.6. Dissemination of Clinical Study Data**

#### **10.1.7. Data Quality Assurance**

- All participant data relating to the study will be recorded on printed or electronic CRF unless transmitted to the sponsor or designee electronically (e.g., laboratory data). The investigator is responsible for verifying that data entries are accurate and correct by physically or electronically signing the CRF.
- The investigator must maintain accurate documentation (source data) that supports the information entered in the CRF.
- The investigator must permit study-related monitoring, and provide direct access to source data documents.
- Monitoring details describing strategy (e.g., risk-based initiatives in operations and quality such as Risk Management and Mitigation Strategies and Analytical Risk-Based Monitoring), methods, responsibilities and requirements, including handling of noncompliance issues and monitoring techniques (central, remote, or on-site monitoring) are provided in the Monitoring Plan.
- The sponsor or designee is responsible for the data management of this study including quality checking of the data.
- The sponsor assumes accountability for actions delegated to other individuals (e.g., Contract Research Organizations).
- Study monitors will perform ongoing source data verification to confirm that data entered into the CRF by authorized site personnel are accurate, complete, and verifiable from source documents; that the safety and rights of participants are being protected; and that the study is being conducted in accordance with the currently approved protocol and any other study agreements, ICH GCP, and all applicable regulatory requirements.
- Records and documents, including signed ICFs, pertaining to the conduct of this study must be retained by the investigator for 5 years after study completion unless local regulations or institutional policies require a longer retention period. No records may be destroyed during the retention period without the written approval of the sponsor. No records may be transferred to another location or party without written notification to the sponsor.

#### **10.1.8. Source Documents**

- Source documents provide evidence for the existence of the participant and substantiate the integrity of the data collected. Source documents are filed at the investigator's site.
- Data reported on the CRF or entered in the eCRF that are transcribed from source documents must be consistent with the source documents or the discrepancies must be explained. The investigator may need to request previous medical records or transfer records, depending on the study. Also, current medical records must be available.

- Definition of what constitutes source data can be found in the SoA data list.

#### **10.1.9. Study and Site Start and Closure**

The study start date is the date on which the clinical study will be open for recruitment of participants.

The first act of recruitment is 15 of February 2020, and will be the study start date.

The sponsor designee reserves the right to close the study site or terminate the study at any time for any reason at the sole discretion of the sponsor. Study sites will be closed upon study completion. A study site is considered closed when all required documents and study supplies have been collected and a study-site closure visit has been performed.

The investigator may initiate study-site closure at any time, provided there is reasonable cause and sufficient notice is given in advance of the intended termination.

Reasons for the early closure of a study site by the sponsor or investigator may include but are not limited to:

- Failure of the investigator to comply with the protocol, the requirements of the IRB/IEC or local health authorities, the sponsor's procedures, or GCP guidelines
- Inadequate recruitment of participants by the investigator
- Discontinuation of further study intervention development

If the study is prematurely terminated or suspended, the sponsor shall promptly inform the Investigators, the IECs/IRBs, the regulatory authorities, and any contract research organization(s) used in the study of the reason for termination or suspension, as specified by the applicable regulatory requirements. The Investigator shall promptly inform the subject and should assure appropriate subject therapy and/or follow-up

#### **10.1.10. Publication Policy**

- The results of this study may be published or presented at scientific meetings. If this is foreseen, the investigator agrees to submit all manuscripts or abstracts to the sponsor before submission. This allows the sponsor to protect proprietary information and to provide comments.

- The sponsor will comply with the requirements for publication of study results. In accordance with standard editorial and ethical practice, the sponsor will generally support publication of multicenter studies only in their entirety and not as individual site data. In this case, a coordinating investigator will be designated by mutual agreement.
- Authorship will be determined by mutual agreement and in line with International Committee of Medical Journal Editors authorship requirements.

## 10.2. **Appendix 2: Adverse Events: Definitions and Procedures for Recording, Evaluating, Follow-up, and Reporting**

### 10.2.1. **Definition of AE**

#### **AE Definition**

- An AE is any untoward occurrence in a patient or clinical study participant, temporally associated with the use of study intervention, whether or not considered related to the study intervention. We will only collect AE's from events related to the anesthetic administration, not from events related to the surgery.

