### 6.1. Study Intervention(s) Administered

EEG-based DoA-mon, Bilateral BIS from Medtronic, to help guide dosage of anesthetic medication perioperatively.

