### 8.2. Adverse Events(AE) and Serious Adverse Events(SAE)

There will be a collection of data on adverse events; movement during surgery, serious hypotension during anesthesia (MAP<60) or awareness with recall after surgery, and other events that is related to the anesthetic administration. We will not collect data on events related to the surgery.

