### **8.2.3. Regulatory Reporting Requirements for SAEs**

- The only unexpected and Serious Adverse Event in our planned study, will be the occurrence of awareness with recall after surgery.
- Prompt notification by the investigator to the sponsor of a SAE is essential so that legal obligations and ethical responsibilities towards the safety of participants and the safety of a study intervention under clinical investigation are met.
- The sponsor has a legal responsibility to notify both the local regulatory authority and other regulatory agencies about the safety of a study intervention under clinical investigation. The sponsor will comply with country-specific regulatory requirements relating to safety reporting to the regulatory authority, Institutional Review Boards (IRB)/Independent Ethics Committees (IEC), and investigators.

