### 10.2.2. **Recording and Follow-Up of AE**

#### **AE**

- When an AE occurs, it is the responsibility of the investigator to review all documentation (e.g., hospital progress notes, laboratory reports, and diagnostics reports) related to the event.
- The investigator will then record all relevant AE information in the CRF.
- It is **not** acceptable for the investigator to send photocopies of the participant's medical records in lieu of completion of the AE CRF page.
- The investigator will attempt to establish a diagnosis of the event based on signs, symptoms, and/or other clinical information. Whenever possible, the diagnosis (not the individual signs/symptoms) will be documented as the AE.

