#### **Assessment of Causality**

- The investigator is obligated to assess the relationship between study intervention and each occurrence of each AE.
- A “reasonable possibility” of a relationship conveys that there are facts, evidence, and/or

arguments to suggest a causal relationship, rather than a relationship cannot be ruled out.

- The investigator will use clinical judgment to determine the relationship.
- Alternative causes, such as underlying disease(s), concomitant therapy, and other risk factors, as well as the temporal relationship of the event to study intervention administration will be considered and investigated.
- The investigator will also consult the Investigator's Brochure (IB) and/or Product Information, for marketed products, in his/her assessment.
- For each AE, the investigator **must** document in the medical notes that he/she has reviewed the AE and has provided an assessment of causality.
- The causality assessment is one of the criteria used when determining regulatory reporting requirements.

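### Serious events enter the trial data only if attributed to the anaesthetic, although the AE definition is independent of relatedness and serious events are not exempted

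*Protocol*

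**What the plan says.** Section 10.2.1 of the protocol defines an AE as any untoward occurrence "temporally associated with the use of study intervention, whether or not considered related to the study intervention". The same bullet then limits what is collected: "We will only collect AE's from events related to the anesthetic administration, not from events related to the surgery".

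Section 8.2, headed for both adverse and serious adverse events, names three events to be collected (movement during surgery, hypotension with MAP below 60 during anaesthesia, awareness with recall) and adds other events related to the anaesthetic. It closes with "We will not collect data on events related to the surgery".

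Section 8.2.2 requires follow-up of all SAEs. In section 10.2.2 the investigator first reviews the documentation, and then "The investigator will then record all relevant AE information in the CRF". On causality the same section says "The investigator is obligated to assess the relationship between study intervention and each occurrence of each AE". The study intervention is described in section 6.1 as "EEG-based DoA-mon, Bilateral BIS from Medtronic, to help guide dosage of anesthetic medication perioperatively". Section 9.4.4 lists adverse events as a safety analysis.

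**The concern.** The definition and the causality paragraph describe the usual order: an event is recorded whatever its cause, and its relatedness is then assessed and documented. The collection rule makes attribution a condition of being in the data. An event judged surgical leaves no trial record, either of itself or of the judgement that excluded it.

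For minor surgical events this is an acceptable economy. For serious events it matters more. A comparison by arm would describe only the events that passed the attribution step, and the trial data could not show whether that step worked alike in both arms.

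**Working it through.** No figure in the plan is in dispute, so the check sets the passages side by side.

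1. **Is there an exception for serious events?** Sections 8.2 to 8.2.3, 10.1.1 and 10.2.1 to 10.2.2 were compared. Section 8.2.2 deals with follow-up, 8.2.3 with notification of the sponsor and authorities, and 10.1.1 with notification of the ethics committee. Each attaches a duty to SAEs. None says that a serious event attributed to surgery is entered in the CRF.

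2. **Which events escape the attribution step?** The three events named in 8.2 are described by what happens and when, so the natural reading is that they are collected without first deciding their cause. The rule therefore bites on every other serious perioperative event.

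3. **Are the two attributions the same?** No. The collection rule separates anaesthetic from surgical origin. The causality paragraph concerns the study intervention, which is EEG-guided monitoring. The causality assessment thus still has a use for the events collected, but it cannot reach an event that was screened out.

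4. **Who makes the split, when, and blinded or not?** The protocol does not say. That it happens before recording is an inference from the wording of the collection rule. Section 10.2.2 gives review and recording to the investigator. The synopsis calls the investigator assessment-masked, but section 6.2 describes that masking only for self-administered cognitive testing. Section 6.2 also has the EEG device covered in the control group only, after the patient is asleep, so theatre staff can know the arm. Section 8.2.1 starts AE collection directly after surgery.

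5. **How large is the gap?** The protocol gives no rate for serious events other than awareness, so the number left out of the 100 patients cannot be calculated.

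**The case against.** The strongest reply is that this is a definition followed by a scope rule. Section 10.2.1 says what an AE is and then which AEs this trial collects, 8.2 states the same scope, and the causality paragraph can be read as applying to each collected AE. Targeted safety collection is a legitimate choice in a short trial of a monitoring strategy, and the events closest to anaesthetic depth are named. This largely stands, and it is why targeted collection of non-serious events need not change. It does not answer the point about serious events: 8.2.2 speaks of all of them, while the collection rule admits only some.

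Four stronger readings are tempting, and the documents do not support them.

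- *That capture is biased between arms.* Nothing shows that attribution differs by arm. Section 6.2 also says that anaesthesia providers are masked from assessing outcome, although it does not say whether AE attribution counts as outcome assessment.
- *That serious surgical events go unreported or cannot be recovered.* The duties in 8.2.2, 8.2.3 and 10.1.1 continue to apply, and section 10.1.8 says of the hospital record: "Also, current medical records must be available". What is lost is the event's place in the trial dataset.
- *That harm from the monitor is excluded.* Section 6.1 has the monitor act by guiding anaesthetic dosage, so harm by that route counts as anaesthetic-related. Section 6.2 connects patients in both arms to the device, so direct sensor effects would not be expected to differ.
- *That section 8.2.3 closes the list of SAEs.* It says "The only unexpected and Serious Adverse Event in our planned study, will be the occurrence of awareness with recall after surgery", which is more plausibly a forecast than a rule.

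**Conclusion.** The point holds in a limited form. As written, a serious perioperative event outside the three named in 8.2 reaches the trial data only if it is attributed to the anaesthetic, by a person whom the protocol does not identify and whose blinding it does not state. The adverse-event comparison in section 9.4.4 therefore cannot show that serious events were captured equally in the two arms.

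This rests on two readings: that the named events are collected whatever their cause, and that not collecting an event means it is not entered in the CRF. No efficacy endpoint or sample-size figure is touched. This is a cheap improvement to safety recording, not a threat to the main results.

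**What to change.** Reconcile sections 8.2, 10.2.1 and 10.2.2.

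- In 8.2 and 10.2.1, state that all serious events from randomisation to the 24-hour visit are recorded whatever their attribution. Enter relatedness to surgery, to the anaesthetic and to the monitoring as separate CRF fields, and report the events by arm.
- Targeted collection of non-serious AEs may stay. Match the definition in 10.2.1 and the causality wording in 10.2.2 to it, so that both refer to the events actually collected.

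The cost is a protocol amendment and a few more CRF entries over about 24 hours in 100 patients, at the collection times already set in 8.2.1. The downside is that some surgical events with no connection to the monitoring will appear in the listing; the relatedness fields let a reader set them aside.

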### 10.2.2. **Recording and Follow-Up of AE**

#### **AE**

- When an AE occurs, it is the responsibility of the investigator to review all documentation (e.g., hospital progress notes, laboratory reports, and diagnostics reports) related to the event.
- The investigator will then record all relevant AE information in the CRF.
- It is **not** acceptable for the investigator to send photocopies of the participant's medical records in lieu of completion of the AE CRF page.
- The investigator will attempt to establish a diagnosis of the event based on signs, symptoms, and/or other clinical information. Whenever possible, the diagnosis (not the individual signs/symptoms) will be documented as the AE.

#### **Assessment of Causality**

- The investigator is obligated to assess the relationship between study intervention and each occurrence of each AE.
- A “reasonable possibility” of a relationship conveys that there are facts, evidence, and/or

arguments to suggest a causal relationship, rather than a relationship cannot be ruled out.

- The investigator will use clinical judgment to determine the relationship.
- Alternative causes, such as underlying disease(s), concomitant therapy, and other risk factors, as well as the temporal relationship of the event to study intervention administration will be considered and investigated.
- The investigator will also consult the Investigator's Brochure (IB) and/or Product Information, for marketed products, in his/her assessment.
- For each AE, the investigator **must** document in the medical notes that he/she has reviewed the AE and has provided an assessment of causality.
- The causality assessment is one of the criteria used when determining regulatory reporting requirements.

#### Follow-up of AEs

- The investigator is obligated to perform or arrange for the conduct of supplemental measurements and/or evaluations as medically indicated to elucidate the nature and/or causality of the AE as fully as possible.
- New or updated information will be recorded in the originally completed CRF.

### 10.3. Appendix 3: Protocol Amendment History

The Protocol Amendment Summary of Changes Table for the current amendment is located directly before the Table of Contents (TOC).

#### Amendment [32173 ver 2.0]: (02.01.20)

This amendment is considered to be substantial based on the criteria set forth in Article 10(a) of Directive 2001/20/EC of the European Parliament and the Council of the European Union.

#### Overall Rationale for the Amendment

This is an amendment of the original protocol sent to, and approved by REK-Helse Sør-Øst, due to a request by the clinical trial unit (CTU) of Oslo University Hospital, in order to make a more precise protocol. This amendment will be sent forwarded to REK after CTU has looked it over.

Section # and Name	Description of Change	Brief Rationale
32173 ver 2.0	Specification of details	

